Symptoms and severity of NVP vary widely, ranging from simple nausea to the most severe form of hyperemesis gravidarum (HG). HG is the most severe stage of nausea and vomiting during pregnancy, accounting for 0.5~2% of all pregnant women^[3]. Although NVP is very common during pregnancy, it is generally considered normal and self-limiting, and its adverse effects on pregnancy are largely underestimated. However, there is evidence that all types of NVP affect the quality of life of pregnant women, and that the magnitude of the impact increases with the frequency of symptoms^[4]. In addition, NVP increases the risk of postpartum depression, and the risk increases with the severity of NVP^[2]. Due to the lack of awareness of NVP and concerns about the teratogenicity of drugs to embryos, NVP treatment is always insufficient, and the choice of medication regimen is conservative, and symptomatic supportive therapy is generally used. The survey found that only 3.64% of patients in China were treated for NVP in the first trimester, which was much lower than the level of the United States (18%) and other countries^[2]. Therefore, pregnant women in China have to endure more discomfort caused by NVP during pregnancy.

The treatment of NVP is generally focused on symptomatic supportive treatment, such as antinausea, rehydration, and correction of acid-base balance. Doxylamine-pyridoxine (Xonvea®, the first-line drug recommended in the guidelines of the United States and the United Kingdom [5-6], considering that it may be related to birth defects, has not been approved for its use in pregnancy in many countries, including China. Due to its special taste, traditional Chinese medicine is difficult for pregnant women to swallow, thus limiting its application in NVP. Acupuncture has good efficacy in the treatment of NVP. In a recent large-sample, multicenter RCT study [7], 352 pregnant patients with moderate or severe NVP were recruited in 13 tertiary hospitals in China (the severity of NVP was determined by the pregnancy-unique quantification of emesis and nausea (PUQE) score, which ranged from 3~15, <6 is mild, 6~12 is moderate, and ≥ 13 is severe), and was treated with acupuncture combined with doxylamine-pyridoxine for 2 weeks. It was found that acupuncture or drugs (docemin-pyridoxine) alone were effective in both moderate and severe NVP, and that the effect of acupuncture was comparable to that of doxymine-pyridoxine, and that the combination of acupuncture and doxymine-pyridoxine may be more effective than their alone. The research results won the top ten academic advances in traditional Chinese medicine in 2023.

Although acupuncture using traditional millineedle has a good effect on NVP, it is inevitably painful when the millineedle is inserted, and the needle sensation of soreness, numbness, swelling and pain during acupuncture is sometimes so strong to cause fear and discomfort in pregnant women, which would produce an adverse effect on pregnancy. Moreover, acupuncture with millineedle needs to be conducted once a day, and pregnant women need to go to the hospital frequently every day, and pregnant women are already inconvenient, which increases the difficulty of pregnant women's medical treatment. Pregnant women, especially in the early stages of pregnancy, should not be stimulated, should recuperate, and maintain physical and mental peace. Therefore, although acupuncture with millineedle has a good effect on NVP, it is still difficult to promote its application in clinical practice.

As a kind of intradermal needle, thumbtack needle (TN) is a method of shallow

puncture and long-term needle. Although the amount of stimulation of TN is weaker than that of millineedle, it has a much longer effect and can produce continuous and stable stimulation, and therefore, the cumulative effect is often better than that of traditional millineedle acupuncture. Moreover, due to the small needle body of TN (the diameter of the needle body is only 0.15 ~ 0.25mm, and the length of the needle body is only 1.2 ~ 2.5mm), it will not hurt the subcutaneous nerves, blood vessels, viscera and other tissues, which is very comfortable and safe to treat, and overcomes the needle sting pain of traditional millineedles. Therefore, TN is especially suitable for some patients who are afraid of needles^[8]. In addition, the TN can be retained for 3~5 days after one treatment, which greatly reduces the duration and frequency of patient's visits. In recent years, some small-sample, non-randomized controlled clinical studies have shown that TN is effective in the treatment of hyperemesis gravidarum^[9-11].

For the treatment of VNP, acupoints such as Zhongwan (CV12), Neiguan (PC6), and Zusanli (ST36) are often used. CV12 is the recruitment point of the stomach, which has the effect of strengthening the spleen and stomach, promoting gastrointestinal peristalsis and emptying. PC6 is the key point for relieving vomiting, rationalizing qi and widening the chest, calming the heart and calming the nerves, and reducing stomach inversion and relieving nausea; Acupuncture ST36 can strengthen the spleen and stomach, nourish qi and nourish blood. Those with disharmony in the liver and stomach are added BL17 or BL18 to relieve the liver and regulate qi, and reconcile the liver and stomach. Those with obstruction of phlegm and dampness are added Fenglong (ST40) to dissolve phlegm and dampness, and those with spleen deficiency and dampness are added to Yinlingquan (SP9) to strengthen the spleen and dispel the dampness.

Since the effect of acupuncture is accumulated over time, the effect is no less than that of traditional milli-needle acupuncture, and the treatment is comfortable, safe and painless, and it can be treated once in 3~5 days, which is simple and easy. Although there are several small, non-randomized clinical trials that suggest that acupuncture has good clinical efficacy in the treatment of VNP, multi-center and large-sample

RCTs are still needed to provide high-quality evidence-based evidence. This project intends to use multi-center, large-sample, randomized, controlled, double-blind clinical trials to observe the effects of nausea and vomiting, quality of life, anxiety and depression, weight change, blood electrolyte levels, liver and kidney function, thyroid function, intravenous infusion therapy, use of additional drugs, hospitalization, pregnancy complications (gestational diabetes and hypertensive diseases), pregnancy outcomes and neonatal outcomes in women with VNP, and evaluate their safety, so as to provide high-quality evidence support for the clinical promotion and application of needles in the treatment of VNP.

2. Study objectives

A multicenter, large-sample, randomized, controlled, double-blind clinical trial was conducted to observe the effects of TN on nausea and vomiting, quality of life, anxiety and depression, weight change, blood electrolyte levels, liver and kidney function, thyroid function, intravenous fluid therapy, use of additional drugs, hospitalization, pregnancy complications, pregnancy outcomes, and neonatal outcomes in women with VNP, and to evaluate its safety.

3. Study content

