3.1.1.2 Women diagnosed with moderate to severe NVP in the first trimester: the

severity of NVP was determined by the PUQE score (see Table 1), and the PUQE score ranged from 3 ~ 15, < 6 was mild NVP, 6 ~ 12 was moderate NVP, and ≥ 13 was severe NVP. PUQE score ≥ 6 may be included in this study;

3.1.1.3 Women voluntarily sign the informed consent form.

Table 1 Quantification of NVP in the US ACOG guidelines

1. In general, how often do you feel nauseous or nauseous each day?				
Never (1)	≤ 1 h (2)	2~3 h (3)	4~6 h (4)	> 6 h (5)
2. In general, how many times a day do you vomit?				
Never (1)	1~2 (2)	3~4 (3)	5~6 (4)	≥ 7 (5)
3. In general, how many times a day do you retch (no contents) ?				
Never (1)	1~2 (2)	3~4 (3)	5~6 (4)	≥ 7 (5)

Total score (add all the points together): Mild NVP: < 6 , moderate NVP: $6 \sim 12$, severe NVP: ≥ 13

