3.2 The intervention program

According to the theory of traditional Chinese medicine, the treatment plan of TN is formulated, and the study protocol follows the CONSORT and STRICTA regulations, and details the number of TN used, the frequency of treatment and the duration of treatment. Both the TN group and the sham TN group were treated with a fixed treatment regimen, which was treated once every 3 days, for a total of 5 treatments for 15 days. During the same period, the blank control group was not given TN or sham TN treatment. All three groups of patients were given pregnancy care and dietary guidance.

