3.2.1 Protocol for TN group

The main acupoints of treatment are Zhongwan (CV12), bilateral Neiguan (SP6), and

bilateral Zusani (ST36), with a total of 5 acupoints. Patients with Qi stagnation should be given Danzhong (CV17) or the Ashi acupoint (Identify the most prominent tender point between the Danzhong (CV17) and Zhongwan (CV12). If such a tender point exists, apply a TN at the tender point, that is, the Ashi acupoint. If no tender point is found, apply the TN at the Danzhong acupoint. Just choose one of the two.), patients with liver and stomach disharmony should be given bilateral Geshu (BL17), patients with phlegm-dampness obstruction should be added bilateral Fenglong (ST40), and patients with weak spleen and stomach should be added bilateral Weishu (BL21). The above acupoints are treated with TN.

The doctor disinfects his hands, strictly disinfects the local skin of the acupoint, applies the disposable sterile TN to the sterilized acupoint, and after a slight pressure, removes the isolation paper (the function of the isolation paper is to avoid direct contact with the sterile glue surface when adhering it to the skin), and press again to ensure that the TN stick the surface of the acupoint firmly. The TN will be kept in the acupoints for 3 days. During the 3-day retention of TN, the patient presses the TN 3 times a day and half a minute per time per acupoint. After 3 days retention of TN, the patient will be instructed to go to the hospital, where the doctor will remove the TN, disinfect the local skin of acupoints and conduct the next treatment of TN. A total of 5 sessions treatment will be applied for a duration of 15 days.

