3.2.2 Protocol for sham TN group

The sham TN will be used for the sham TN group. Even though the appearance and shape of sham TN are similar to the real TN, the sham TN has no needle body. Therefore, the sham TN does not produce a needle-like effect of TN

The acupoints of sham TN group are the same as those of TN group. The use of sham TN was the same as that of the TN group. After 3 days retention of sham TN, the patient was instructed to go to the hospital, where the doctor removed the sham TN, and conducted the next treatment after local skin disinfection. A total of 5 treatments were given for a duration of 15 days.

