3.2.3 Record for the treatment

The treatment date, time and the name of the acupuncturist are recorded when the patient receives TN or sham TN treatment. No treatment is given to the blank control group, but the date and times of the inquiry of blank control group are also recorded. During the treatment, the local hematoma or turquoise, pain or skin allergies that may occur during the treatment, as well as other discomforts after the treatment (nausea, vomiting, palpitations, dizziness, headache, anorexia and insomnia), should be recorded in detail and disposed in time.

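### The three-arm trial is called double-blind without restriction although blank-control women cannot be blinded, and section 3.6.2 tests three groups where 3.6.1 names and sizes TN versus sham TN

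*Protocol*

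**What the plan says.** **Blinding label.** The protocol calls the trial double-blind twice without naming the arms this covers. The last background paragraph reads "This project intends to use multi-center, large-sample, randomized, controlled, double-blind clinical trials to observe the effects", and section 2 (Study objectives) reads "A multicenter, large-sample, randomized, controlled, double-blind clinical trial was conducted to observe the effects of TN".

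**Arms.** Section 3.1 randomises to TN, sham TN and blank control. Section 3.2 says "the blank control group was not given TN or sham TN treatment", and 3.2.3 repeats "No treatment is given to the blank control group". What the arms share is background care: "All three groups of patients were given pregnancy care and dietary guidance".

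**Devices.** In the TN arm, "the patient presses the TN 3 times a day and half a minute per time per acupoint" (3.2.1). For the sham arm, "The use of sham TN was the same as that of the TN group" (3.2.2). The sham resembles the real device but lacks the needle.

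**Outcome.** The primary outcome is the change in PUQE score from baseline to day 15 (3.3.1). PUQE is built from the woman's own answers, for example "In general, how many times a day do you vomit" (3.1.1.2, Table 1).

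**Comparison.** Section 3.6.1 uses the change in PUQE to compare TN with sham TN and bases the sample size on that pair. Section 3.6.2 describes the test of PUQE change as one across three groups, and does not say which contrast carries the efficacy conclusion.

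**The concern.** A woman in the blank control arm has nothing on her skin and knows it. She then scores her own nausea, vomiting and retching. Every comparison with that arm is therefore unblinded on a self-reported primary outcome, and the unrestricted label claims a property that the three-arm design does not have.

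The device arms also differ from blank control in more than the needle. They wear a device, press it three times a day at each acupoint, and may expect benefit. TN versus blank or sham TN versus blank mixes these influences with any needle effect. Only TN versus sham TN separates them.

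Section 3.6.1 is built on that contrast, but the test written in 3.6.2 answers a different question: whether any of the three means differ. A significant answer could come wholly from device versus no device. Reported under a double-blind label, it could be taken as proof that the needle works.

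**Working it through.** **1. Which contrasts can be participant-blind**

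| Contrast | Device in both arms? | Participant-blind possible? |
|---|---|---|
| TN vs sham TN | Yes, similar appearance (3.2.2) | Yes |
| TN vs blank | No (3.2, 3.2.3) | No |
| Sham TN vs blank | No (3.2, 3.2.3) | No |

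**2. Which contrast 3.6.1 sizes**

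Inputs from 3.6.1: mean falls 4.9 (TN) and 4.0 (sham TN); SDs 2.4 and 2.7; two-sided alpha 0.05; power 0.80; 1:1.

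- Difference: 4.9 − 4.0 = 0.9.
- Average variance: (2.4² + 2.7²)/2 = (5.76 + 7.29)/2 = 6.525, so SD = 2.554.
- Normal approximation: n = 2 × (1.960 + 0.842)² × 6.525 / 0.9² ≈ 126.5, so 127 per group. The t-based solution is 127.4, so 128. This reproduces the protocol's figure.
- Power at 128 per group: about 80%.
- Enrolment: 128/(1 − 0.20) = 160 per group, and 2 × 160 = 320.

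This is a two-group calculation. Blank control enters neither the formula nor the total, so the 80% power belongs to TN versus sham TN.

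**3. What a three-group test responds to when the needle has no effect**

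Assumptions:

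- The test is a one-way ANOVA, because 3.6.2 names no three-group test for PUQE.
- TN and sham TN have the same mean fall, larger than the blank fall by a gap g. The protocol gives no fall for blank control, so g is varied. The value 0.9 is used only because it equals the TN–sham difference in 3.6.1.
- n = 128 per group. SD is 2.7, with 2.4 as the alternative (both from 3.6.1).

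Degrees of freedom are 2 and 3 × 128 − 3 = 381; the critical F at 5% is 3.02. With two means at g and one at 0, the noncentrality is λ = n × (2/3) × g² / SD². For example, g = 0.9 and SD 2.7 give 128 × (2/3) × 0.81/7.29 = 9.48.

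| Gap g | λ, SD 2.7 | Power, SD 2.7 | λ, SD 2.4 | Power, SD 2.4 |
|---|---|---|---|---|
| 0 | 0 | 5% | 0 | 5% |
| 0.5 | 2.93 | 31% | 3.70 | 39% |
| 0.9 | 9.48 | 79% | 12.00 | 88% |
| 1.5 | 26.34 | 99.7% | 33.33 | >99.9% |

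Simulation at SD 2.7 (20,000 runs) gave 0.051, 0.314, 0.786 and 0.998. In the same setting a direct two-sided TN versus sham TN test rejects in 5% of trials whatever g is.

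**The case against.** **The percentages are not false positives.** If TN equals sham TN and blank differs, the three-group null hypothesis is false and rejecting it is correct. This stands. The figures are power to detect a true device-versus-blank difference. A reader might infer a type I error of 31% to 99.7%, and the protocol does not support that. If the three-group test were followed by TN versus sham TN at 5%, simulation at SD 2.7 puts false TN-versus-sham claims at about 2.6%, 3.9%, 4.7% and 5.0% for gaps of 0, 0.5, 0.9 and 1.5. The harm arises only if the three-group result is read alone.

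**Section 3.6.1 already names the efficacy comparison.** This is also true. Sizing on one contrast and testing all arms can coexist, and a statistical analysis plan that is not at hand may set out pairwise follow-up. A reader might infer that the sample size is wrong or the primary contrast absent; neither follows. What remains is that 3.6.2 writes the primary test as a three-group difference and does not carry the 3.6.1 contrast forward.

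**The label is loose wording that nobody would misread.** In part. Sections 3.2 and 3.2.3 are open about the blank arm receiving nothing. But the claim appears twice, and no sentence limits it to the device arms.

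**Staff and safety reports.** A reader might infer from 3.1 that staff are unblinded, because enrolling researchers obtain grouping information, or from 3.5 that double-blind board reports are impossible. Neither is supported. Section 3.1 does not say whether that information is coded, and arms can be shown by code in board reports. These are minor clarifications, not part of the error.

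**Conclusion.** The point holds in this form. Double-blind is stated for a three-arm trial in which one arm cannot be participant-blind on a self-reported primary outcome; the label can hold at most for TN versus sham TN. The primary test in 3.6.2 is not the contrast that 3.6.1 names and sizes, and it can be significant with no needle effect.

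The misstatement of blinding follows from the text and needs no assumption beyond the fact that a woman knows whether she wears a device. The size of the interpretive problem does rest on assumptions: the ANOVA, 128 evaluable per group, and a device-minus-blank gap that the protocol does not give. With no gap, the three-group test rejects at 5%; the problem grows with the gap.

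The 128 per group is sound for TN versus sham TN. The correction should be made before results are read, because it determines what a positive result can support.

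**What to change.** 1. In the last background paragraph and in section 2, replace the unrestricted claim with wording such as: *participant-blinded for TN versus sham TN; comparisons with blank control are not participant-blinded*. If double-blind is kept, apply it to TN versus sham TN only.
2. In 3.6.2, state: *the primary comparison is TN versus sham TN, as in 3.6.1, at two-sided 0.05; the three-group test and comparisons with blank control are supportive and cannot isolate a needle effect*.

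While editing, 3.1 could say which staff are blinded to assignment, and 3.5 could say what blinding means for the board reports. Both are optional clarifications.

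**Cost.** Text changes only, with no added patients or visits. The blinding claim becomes more modest, and comparisons with blank control lose standing as primary evidence.

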3.1 The selection and exclusion of subjects

We will choose moderate or severe 320 VNP patients who take a visit during Oct. 2024 to Oct. 2028 to the departments mentioned below: Department of Integrated Traditional Chinese and Western Medicine, Tongji Hospital, Tongji Medical College, Huazhong University of Science and Technology, Wuhan, Hubei, China; Fujian Provincial Maternal and Child Health Care Hospital; Jingzhou Traditional Chinese Medicine Hospital, Jingzhou, Hubei, China; Qianjiang Maternal and Child Health Care Hospital, Qianjiang, Hubei, China; Xiaogan Maternal and Child Health Care Hospital, Xiaogan, Hubei, China; Qianjiang Central Hospital, Qianjiang, Hubei, China; Shiyan People's Hospital, Shiyan, Hubei, China; Wuhan Jinxin Gynecology

and Obstetrics Hospital of Integrative Medicine, Wuhan, Hubei, China; Xiangyang Traditional Chinese Medicine Hospital, Xiangyang, Hubei, China; Suizhou Maternal and Child Health Care Hospital, Suizhou, Hubei, China; Nanzhang County Traditional Chinese Medicine Hospital, Nanzhang, Hubei, China; Dongchangfu District Maternal and Child Health Care Hospital of Liaocheng City, Liaocheng, Shandong, China; Xiangyang Central Hospital, Xiangyang, Hubei, China; Aksu Prefecture Maternal and Child Health Hospital, Aksu, Xinjiang, China.

The age of the patients is between 20 to 45 years. According to the Network version of the central randomization system, patients are allocated randomly as 1:1 to TN group, sham TN group and blank control group with 160 patients in each group. The network version of the central randomization system designs the random parameters. The clinical researchers log in the system and input the information of the subjects to be enrolled, after that they can obtain the random number and grouping information assigned by the system. The randomization protocol and the parameters set during the generation of the protocol are collectively called blind substrates, and are all kept by people who are not involved in the process of treatment, evaluation and statistical analysis.

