3.3 Outcome measures

3.3.1 Primary outcome measure

PUQE scores were evaluated before treatment and on days 3, 6, 9, 12, and 15 of treatment. The primary outcome measure was the change of PUQE score on day 15 at the end of the treatment when compared with the baseline.

3.3.2 secondary efficacy endpoints

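### The protocol claims a double-blind trial, but shows each woman's group to the enrolling researchers and describes neither a coded device nor a blinded PUQE assessor

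*Protocol*

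**What the plan says.** Section 2 (Study objectives) describes a "randomized, controlled, double-blind clinical trial was conducted to observe the effects of TN", and section 3.5 promises the oversight board safety reports on a double-blind basis.

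Section 3.1 sets out who sees what. The clinical researchers log in and enter the woman's details, and "after that they can obtain the random number and grouping information assigned by the system". The randomisation scheme and its parameters, by contrast, "are all kept by people who are not involved in the process of treatment, evaluation and statistical analysis".

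On the device, section 3.2.2 says: "Even though the appearance and shape of sham TN are similar to the real TN, the sham TN has no needle body". The background section gives the length of the real needle body as 1.2 to 2.5 mm. Sections 3.2.1 and 3.2.2 have a doctor apply the device, remove it after 3 days and apply the next, for five sessions over 15 days.

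On the outcome, section 3.3.1 says that "PUQE scores were evaluated before treatment and on days 3, 6, 9, 12, and 15 of treatment". The change at day 15 is primary. No assessor is named. The items in Table 1 (section 3.1.1.2) ask the woman about her hours of nausea and her counts of vomiting and retching.

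**The concern.** Withholding the scheme protects the sequence of future assignments. It does not hide the group of a woman already randomised, and section 3.1 gives that group to clinical staff. The person handling the device has a second route to the same knowledge, because one version has a needle and the other does not.

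The PUQE is a recalled, subjective score. If someone who knows the group asks the questions, or speaks with the woman before she answers, tone or prompting can shift the answers in one arm. The sham arm exists to remove that kind of difference from the primary comparison. The protocol contains no rule that prevents it, and a bias in the collected scores cannot be taken out in the analysis.

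**Working it through.** **1. Who is blinded, by role, from the text**

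| Role | What the protocol provides |
|---|---|
| Woman, TN or sham | Sham similar in appearance and shape (3.2.2); nothing cited here unblinds her |
| Woman, blank arm | No device, so she cannot be blinded (3.2, 3.2.3) |
| Enrolling researcher | Given the group (3.1) |
| Doctor applying the device | Handles a device with or without a needle body (3.2.1, 3.2.2); no coding described |
| Person recording the PUQE | Not named (3.3.1) |
| Analyst | Kept from the scheme and parameters; nothing said about individual assignments (3.1) |

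No staff role is shown to be blind to an individual woman's group.

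**2. Do device visits and PUQE days coincide?** The protocol does not date the removals. Assume the first application is on day 0. Five sessions at 3-day intervals then give applications on days 0, 3, 6, 9 and 12, and removals on days 3, 6, 9, 12 and 15. The removal days are the five post-baseline PUQE days. Day 15, the primary time point, is a removal only. Baseline PUQE is an entry criterion, so it precedes allocation and is not affected.

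**3. The plan's own sample size.** Inputs from section 3.6.1: mean falls of 4.9 (SD 2.4) and 4.0 (SD 2.7), two-sided α = 0.05, power 0.80.

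- Difference: 4.9 − 4.0 = 0.9.
- Pooled variance: (2.4² + 2.7²)/2 = (5.76 + 7.29)/2 = 6.525. Pooled SD: √6.525 = 2.554.
- n per group = 2 × (1.96 + 0.8416)² × 6.525 / 0.9² ≈ 126.5, so 127. The t-based solution is 127.4, so 128, which is the plan's figure.
- Allowance for dropout: 128 / (1 − 0.20) = 160, also the plan's figure.

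The combined variance of 2.0 in that section does not match these SDs. That is a separate matter and is not used here.

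**4. Illustration of sensitivity.** The documents give no size for an assessment bias, so b below is assumed. With no true effect and 128 per group:

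- SE = 2.554 × √(2/128) = 2.554 × 0.125 = 0.3193.
- P(significant) = 1 − Φ(1.96 − b/SE) + Φ(−1.96 − b/SE).

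| Assumed bias b (points) | b/SE | P(significant) |
|---|---|---|
| 0 | 0 | 5% |
| 0.2 | 0.63 | 10% |
| 0.3 | 0.94 | 16% |
| 0.5 | 1.57 | 35% |
| 0.9 | 2.82 | 80% |

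If all 160 per group were observed, biases of 0.2 and 0.3 would give about 11% and 18%. The last row of the table equals the planned power, because a bias of 0.9 cannot be told apart from the planned effect.

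**The case against.** Several points on the other side are fair.

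- **The device.** A reader might infer that the two devices are visibly different. The text does not say so: section 3.2.2 calls them similar in appearance and shape. That a doctor notices the absence of a 1.2 to 2.5 mm needle body is probable, but it is an inference.
- **The assessor.** A reader might infer that the unblinded doctor takes the PUQE. Section 3.3.1 names nobody. The woman supplies the answers, she is the intended blinded party between TN and sham, and section 3.1 lists evaluation as a function separate from treatment. A blinded assessor is not excluded; none is described.
- **Acupoints.** A reader might infer that the group is known before added points are chosen. The order is not stated, and section 3.2.2 gives the sham arm the same acupoints as the TN arm. Nothing requires the pattern diagnosis to come first, and that is as far as the point goes.
- **The word fixed.** Section 3.2 says "Both the TN group and the sham TN group were treated with a fixed treatment regimen", and a reader might see a conflict with the pattern-based points in 3.2.1. The sentence goes on to give the interval and number of sessions, so it reads naturally as a fixed schedule. There is no contradiction to report.
- **The operator.** An unblinded operator is hard to avoid with a needle device. That is true, and it is a reason to describe the blinding accurately rather than to claim more.
- **The bias sizes.** They are assumed, and the calculation is not evidence that bias will occur.

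After all this, two things stand: the group is disclosed to clinical researchers, and no safeguard is written for the scores.

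**Conclusion.** The concern holds in this limited form. The protocol claims a double-blind trial, but following section 3.1 as written does not deliver the staff side of that blind. The enrolling researchers are given each woman's group, the operator can probably identify the device, the blank arm is open, and no blinded assessor or coded device is described. The documents do not show that blinding of the woman between TN and sham fails, or that anyone who knows the group will in fact record the score.

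No stated figure changes; 128 and 160 both reproduce. The stake is the primary TN-sham contrast of 0.9 points with a pooled SD of 2.55. Under the assumed biases of 0.2 to 0.5 points, the false-positive rate would be about 10% to 35% instead of 5%. The match between device visits and PUQE days rests on counting the first application as day 0.

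**What to change.** (a) In 3.1, limit access to the group to the person who applies the device. Anyone who collects or analyses outcomes sees only a subject number.

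(b) In 3.3, have the woman complete the PUQE and the questionnaires herself on arrival, before contact with anyone who knows her group and, in the TN and sham arms, before the device is removed. Use the same form and timing in all three arms.

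(c) Replace the general double-blind claim with a statement by role: participant-blind for TN versus sham, operator unblinded, blank arm open. Align the safety-reporting sentence in 3.5 with it.

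(d) Record each woman's pattern diagnosis before logging in to the randomisation system. The rules for choosing acupoints stay as they are.

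The cost is protocol wording, a change of user rights in the randomisation system and a slightly stricter visit order. Self-completion should avoid the need for a separate assessor. At a site where one person both enrols and treats, that person is the unblinded operator and should not handle the outcome forms. The downside is a weaker, but accurate, blinding label.
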